13.6.5. Healthcare Resource Use**Currency Conversion**

- To convert local currencies into a comparable combinable unit, all currencies will be converted into US Dollars (USD), at the exchange rate obtained from xe.com reported for 15 February 2015 (accessed on 23JUL2016). This date was chosen as a midpoint in the study.

Currency	USD per unit
Brazilian Real	0.3528270266
Peruvian Sol	0.3272251315

Currency Conversion		
	Colombian Peso	0.0004193751
	Thai Baht	0.0306701426
	Vietnamese Dong	0.0000468165

13.6.6. Exploratory G6PD and CYP-2D6 Genotype Analyses

G6PD Mutations
Emory Genetics Laboratory will provide a description of the G6PD mutation (such as Vanua Lava (c.383T>C, p.L128P- exon 5) het). In addition, the WHO classification of G6PD enzyme deficiency will be provided for each mutation observed
CYP2D6 Activity and Metabolizer Phenotype

 Quest Nichols laboratory will provide CYP2D6 *alleles which will be used to derive metabolizer class (PM, IM, EM, UM) Each of the two CYP2D6 *alleles, comprising the genotype, will be assigned a value relative to its activity compared to the *1 reference allele: 
 Value of 0 for null activity alleles: *3, *4, *4xN, *5, *6, *7, *8, *11, *12,*13, *15, *16, *19, *20, *21, *38, *40, *42, *56B Value of 0.5 for reduced activity alleles: *9, *10, *17, *29, *41 Value of 1 for fully functional alleles: *1, *2, *33, *35 Value of 2 for fully functional alleles carrying gene duplications: *1xN, *2xN, *33xN, *35xN For all *alleles that are not captured above, the activity score will be determined prior to unblinding the data. Alleles denoting gene duplications, represented by 'xN', will receive double the non-duplicated value. For example *1xN will receive a value of 2 whereas *1 receives a value of 1. The CYP2D6 Activity Score (AS) [Gaedigk, 2008] is then calculated as the sum of activity values from the two alleles comprising the genotype. For example, a subject with 2 null alleles will have an AS of 0; one null and one reduced activity allele will have a score of 0.5; or one null allele and one fully functional allele will have an AS of 1. The CYP2D6 phenotype will be classified based on the AS and follows the Dutch Pharmacogenomics Working Group [DPWG] classification scheme. 
 Poor metabolizer (PM) if AS = 0 Intermediate metabolizer (IM) if AS = 0.5 or 1 Extensive metabolizer (EM) if AS is 1.5 or 2 Ultrametabolizer (UM) if AS \geq2.5

13.7. Appendix 7: Premature Withdrawals & Handling of Missing Data

13.7.1. Premature Withdrawals

Element	Reporting Detail
General	
 Subject study completion is defined as a subject that does not withdraw from the study and attends the Day 180 visit. Withdrawn subjects will not be replaced in the study. All available data from subjects who were withdrawn from the study will be listed and all available planned data will be included in summary tables and figures, unless otherwise specified.

13.7.2. Handling of Missing Data

Element	Reporting Detail
General	
 Missing data occurs when any requested data is not provided, leading to blank fields on the collection instrument : 
 These data will be indicated by the use of a "blank" in subject listing displays. Unless all data for a specific visit are missing in which case the data is excluded from the table. Answers such as "Not applicable" and "Not evaluable" are not considered to be missing data and should be displayed as such.
Outliers	
 Any subjects with outlying results may be excluded in additional ad hoc summaries and/or statistical analyses. These will be documented along with the reason for exclusion in the clinical study report, but the primary conclusions will remain based on the full population sets.

13.7.2.1. Handling of Missing Dates

Element	Reporting Detail
General	Partial dates will be displayed as captured in subject listing displays.
Adverse Events	
 It is not possible to record partial dates in the eCRF for AEs. Completely missing start or end dates will remain missing, with no imputation applied. Consequently, time to onset and duration of such events will be missing. AEs with entirely missing or unknown start dates will be assumed to be treatment emergent for reporting. AEs with missing end dates are not anticipated to affect reporting.
Concomitant medications	
 Where the start or stop date of a concomitant medication record is entirely unknown and is totally missing at the time of reporting, the eCRF flags 'Taken prior to study?' and 'Ongoing medication?' will be used in order to derive whether it is prior or concurrent. If these flags are also missing, then it will be assumed that it is concurrent.

Element	Reporting Detail
	
 In the event that use of the same medication is recorded at more than one visit (and if this has not been collapsed to one record), the eCRF flags will be cross-checked for both records.

13.7.2.2. Handling of Partial Dates

Element	Reporting Detail
Concomitant Medications	
 Partial dates for any concomitant medications recorded in the CRF will be imputed using the following convention: 
 If the partial date is a start date, a '01' will be used for the day and 'Jan' will be used for the month If the partial date is a stop date, a '28/29/30/31' will be used for the day (dependent on the month and year) and 'Dec' will be used for the month. The recorded partial date will be displayed in listings.
Adverse Events	
 It is not possible to record partial dates in the eCRF for AEs.
Date of birth	
 Where a subject's date and month of birth is not known, the investigator has been asked to enter them as 30th June, and where month is known but date is unknown, the investigator has been asked to enter the 15th. Thus all subjects should have an actual or an assumed date of birth entered on the eCRF. In the event that any partial dates do occur for date of birth, age should be calculated using 30th June for an unknown date and month, and 15th for an unknown date only. Only the year will be displayed in listings.

13.7.2.3. Handling of Missing Data for Statistical Analysis

Element	Reporting Detail
Incidence of Haemolysis	
 For the primary analysis only observed data will be used. A sensitivity analysis will be performed where missing haemolysis data before Study Day 17 will be imputed as 'haemolysis=YES'.
Relapse-free efficacy and time to event endpoints	
 For all analyses of the mITT population, subjects will not be excluded from any statistical analyses. From the Day 29 assessment onwards, subjects who have not relapsed but fail to have an evaluable parasite smear within the visit window for every scheduled visit will be excluded from the PP population. See Section 13.6.4 for further details on how missing assessments will be censored.
Derived variables	
 For derived variables, details of how any missing eCRF data will be handled are provided in Section 13.6.

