6.4. Safety

The timing and details of all safety assessments are provided in the Time and Events table in Section 6. Additional details on specific assessments are provided below. Blinded safety information will be reviewed on a monthly basis by a GSK/MMV safety review team.

There are two co-primary safety endpoints in this study: clinically relevant hemolysis will be compared between the two treatment groups in all subjects, and in 50 female subjects with moderate G6PD deficiency ($\geq 40\%$ to $< 70\%$ of the median site value).

Information on concomitant medication will be collected daily while the subject is an in-patient, at all scheduled treatment and follow-up visits, and if there is a relapse or premature withdrawal visit.

Physical examinations will be performed daily during in-patient days, on each scheduled treatment and follow-up visit at Days 8, 15, 22, 29, 60, 90, 120, 150 and 180 and if there is a relapse or premature withdrawal visit.

Vital signs will be performed twice daily whilst an in-patient and on follow-up visits at Days 8, 11, 15, 22, 29, 60, 90, 120, 150 and 180 and if there is a relapse or premature withdrawal visit.

12-lead ECG will be performed at screening, 12 hours (± 30 minutes) after the first dose of blinded study medication, and at Day 29. ECG assessments will also be conducted in cases of relapse or early withdrawal. ECGs will be performed in triplicate at screening but single ECGs will be performed subsequently as indicated in [Table 2](#) unless prolonged QTc is seen.

Clinical chemistry and hematology samples will be analyzed by local laboratories. Evaluations will be made at screening, treatment Days 3, 5, 8, 11, 15 and follow-up Days 22, 29, 60, 90, and 120. These assessments will also be performed if there is a relapse or withdrawal visit. The panel of tests to be analyzed are detailed below in [Table 3](#) and [Table 4](#). All laboratory data will be used for the purpose of safety analysis and reporting for this study. Any laboratory tests the attending physician or investigator deems necessary for the care and safety monitoring of the study subjects will be conducted by the local laboratory. All laboratory results that are considered clinically significant should be recorded as AEs.

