8.2. Study Design Considerations

8.2.1. Sample Size Assumptions

The sample size of 300 is based on the regulatory requirement to obtain an appropriate total safety database in subjects treated with TQ/CQ at the selected dose, given that subjects are randomized to TQ/CQ: PQ/CQ on a 2:1 ratio.

Included in this sample is a key subgroup of a minimum of 50 female subjects with moderate (40-70%) G6PD enzyme activity. This subgroup will be used to assess the risk to G6PD heterozygous deficient females who may be misclassified by a G6PD POCT and inadvertently treated with TQ.

[figure not shown]
The proportion of heterozygous subjects in this subgroup who will meet the primary endpoint of clinically relevant hemolysis when treated with either TQ or PQ is assumed to be 50%. A sample size of 30 such subjects treated with TQ will provide precision of 18% for the 95% confidence interval. Similarly, sample size of 15 subjects treated with PQ will provide a precision of 25%.

With 50% of the subjects in the subgroup and none of the other subjects assumed to meet the primary endpoint, we expect 8% of the total cohort to have a clinically relevant hemolysis. The 200 subjects in the TQ group will provide a precision of 4% and the 100 subjects in the PQ group precision of 5% for the 95% CI.

The power for testing a difference in proportion between the two treatment groups will be provided retrospectively.

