7.1.2. Planned Safety Statistical Analyses

Primary Statistical Analyses
Endpoint(s)

 Occurrence of clinically relevant haemolysis in all subjects. See Section 13.6.3 for derivation of clinically relevant haemolysis.
Model Specification

 No formal statistical analyses will be performed as the incidence of clinically relevant haemolysis is expected to be low. 95% confidence intervals for the proportion of subjects (\hat{p}) with clinically relevant haemolysis in each treatment group (i, j) will be based in the Wilson score: $\left(\hat{p}_i + z_{\alpha/2}^2 / 2n_i \pm z_{\alpha/2} \sqrt{(\hat{p}_i(1 - \hat{p}_i) + z_{\alpha/2}^2 / 4n_i) / n_i} \right) / 1 + z_{\alpha/2}^2 / n_i$ This can be obtained in SAS using the BINOMIAL option in PROC FREQ. The Newcombe method based on the Wilson score will be used to calculate the 95% confidence interval for the difference in proportion ($\hat{p}_i - \hat{p}_j$) (Newcombe, 1998): $\text{lower limit} = (\hat{p}_i - \hat{p}_j) - \sqrt{(\hat{p}_i - L_i)^2 + (U_j - \hat{p}_j)^2}$ $\text{upper limit} = (\hat{p}_i - \hat{p}_j) + \sqrt{(U_i - \hat{p}_i)^2 + (\hat{p}_j - L_j)^2}$ where U and L represent the upper and lower limit respectively of the corresponding

Primary Statistical Analyses

proportion. This can be obtained in SAS using the RISKDIFF option with (CL=(NEWCOMBE)) in PROC FREQ.

Results Presentation

 Table 3.1, Figure 3.1: The proportion of subjects with clinically relevant haemolysis in each treatment group will be presented together with a confidence interval based on the Wilson score The difference between treatment groups in the proportion of subjects with clinically relevant haemolysis in each treatment group will be presented together with a confidence interval based on the Newcombe method (tables only) Due to the low number of G6PD deficient females expected, they will be included in the primary analysis but their data will be listed separately.

Sensitivity and Supportive Statistical Analyses

 To assess the impact of missing data, a sensitivity analysis will be performed using imputed data where data is missing, as described in Section 13.7.2.3 and the methodology detailed above (Table 3.2).

Further safety analyses are described in Section 8.2.

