13.3. Appendix 3: Assessment Windows

13.3.1. Definitions of Assessment Windows for All Analyses

Visit	Analysis Window	
	Beginning Timepoint	Ending Timepoint
Day 1	Study Day 1	Study Day 1
Day 2	Study Day 2	Study Day 2
Day 3	Study Day 3	Study Day 4
12 hours post randomised treatment ¹	11.5 hours post first dose of randomised treatment (Study Days 1-4)	12.5 hours post first dose of randomised treatment (Study Days 1-4)
Day 5	Study Day 5	Study Day 6
Day 8	Study Day 7	Study Day 9
Day 11	Study Day 10	Study Day 12
Day 15	Study Day 13	Study Day 17
Day 22	Study Day 19	Study Day 25
Day 29	Study Day 26	Study Day 32
Day 60	Study Day 53	Study Day 67
Day 90	Study Day 83	Study Day 97
Day 120	Study Day 110	Study Day 130
Day 150	Study Day 140	Study Day 160
Day 180	Study Day 166	Study Day 201

¹For ECG parameters only

For all data summarised by visit, the nominal visit description will be used. Unscheduled and withdrawal visit data will be slotted into a scheduled visit window, if no competing visit exists within the window. If there are multiple assessments within the same window which are not unscheduled visits, the earliest result will be used in the summaries.

Note that the 12 hours post dose window is used only for the ECG parameters. If there are multiple measurements within the acceptable window, the assessment closest to the nominal visit description will be used in the summaries. If triplicate readings were taken, the mean of the triplicates will be used in the summaries.

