13.6.3. Safety

Clinically Relevant Haemolysis

 • Clinically relevant haemolysis is defined as: a decrease in haemoglobin of $\geq 30\%$ or >30 g/L (>3 g/dL) from baseline; or, an overall drop in haemoglobin below 60 g/L (6.0 g/dL) at any visit after the first dose of study medication. • If a subject has any missing post-baseline haemoglobin data up to Study Day 17, the primary endpoint will be set to missing. • A subject will be classified as not having haemolysis at any visit if they do not meet the above haemoglobin criteria and no visits are missing up to Study Day X. • See Section 13.7.2.3 for further handling of missing data.

ECG Parameters
RR Interval 
 • ECGs are manually read, the RR value preceding the measurement QT interval should be a collected value so no derivation is required.
Corrected QT Intervals 
 • QTcF will be derived at the site and entered into the eCRF.

Adverse Events

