13.14.6. Safety Tables

Safety: Tables					
No.	Population	IDSL / TST ID / Example Shell	Title	Programming Notes	Deliverable
Incidence of haemolysis					
3.1.	Safety	SA40	Analysis of Incidence of Haemolysis		Headline
3.2.	Safety	SA40	Analysis of Incidence of Haemolysis (Missing data sensitivity analysis)	Exclude 'Missing' row. Add footnote to say 'Missed visits up to Study Day 17 have been imputed as Yes'	Headline
Adverse Events (AEs)					
3.3.	Safety	AE1	Summary of All Treatment Emergent Adverse Events by Treatment by System Organ Class	ICH E3 Add footnote: 'Events are ordered based on Total incidence'	SAC
3.4.	Safety	AE3	Summary of Common Treatment Emergent Adverse Events (>=5% in Any Treatment Group) by Preferred Term	ICH E3, GSK CTR Order events in descending order by incidence in TQ+CQ arm only. Add footnote: 'Events are ordered based on incidence in TQ+CQ arm'	Headline
3.5.	Safety	AE15	Summary of Common (>=5% in Any Treatment Group) Non-serious Treatment Emergent Adverse Events by System Organ Class and Preferred Term (Number of Subjects and Occurrences)	FDAAA, EudraCT	SAC
3.6.	Safety	AE3	Summary of All Drug-Related Treatment Emergent Adverse Events by Treatment by Preferred Term	GSK CTR Order events in descending order by incidence in TQ+CQ arm only. Add footnote: 'Events are ordered based on incidence in TQ+CQ arm'	Headline
3.7.	Safety	AE5	Summary of Treatment Emergent Adverse Events by Maximum Intensity	Add footnote: 'Events are ordered based on Total incidence'	SAC

Safety: Tables					
No.	Population	IDSL / TST ID / Example Shell	Title	Programming Notes	Deliverable
3.8.	Safety	AE3	Summary of All Treatment Emergent Adverse Events by Treatment by Preferred Term	Order events in descending order by incidence in TQ+CQ arm only. Add footnote: 'Events are ordered based on incidence in TQ+CQ arm'	SAC
3.9.	Safety	AE3	Summary of Treatment Emergent Adverse Events with Onset On or Prior to Study Day 29	Add footnote: 'Events are ordered based on Total incidence'	Headline
3.10.	Safety	AE3	Summary of Treatment Emergent Adverse Events with Onset Date in Month 2 or 3	Add footnote: 'Events are ordered based on Total incidence'	SAC
3.11.	Safety	AE3	Summary of Treatment Emergent Adverse Events with Onset On After Month 3	Add footnote: 'Events are ordered based on Total incidence'	SAC
Serious and Other Significant Adverse Events					

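### The only missing-data sensitivity analysis of the primary endpoint imputes haemolysis in both arms; it caps each arm's incidence but does not bound the TQ–PQ difference, and missed visits could dominate it

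*Supplement*

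**What the plan says.** All references are to the latest RAP (21 February 2017) and protocol amendment 5.

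- **What counts as missing** (RAP 13.6.3): "If a subject has any missing post-baseline haemoglobin data up to Study Day 17, the primary endpoint will be set to missing".
- **Primary analysis** (RAP 13.7.2.3): "For the primary analysis only observed data will be used". This is Table 3.1.
- **Purpose of the sensitivity analysis** (RAP 7.1.2): "To assess the impact of missing data, a sensitivity analysis will be performed using imputed data where data is missing". It uses the same Wilson intervals per arm and Newcombe interval for the difference.
- **Rule** (RAP 13.7.2.3): "missing haemolysis data before Study Day 17 will be imputed as" haemolysis, with no distinction by arm.
- **Output** (RAP 13.14.6, Table 3.2, a Headline table): the row for missing subjects is dropped and the footnote reads "Missed visits up to Study Day 17 have been imputed as Yes". No other missing-data analysis of this endpoint is listed.
- **Draws concerned** (protocol 6.4): after screening, haemoglobin is taken on "treatment Days 3, 5, 8, 11, 15", so five scheduled draws fall in the period.
- **Mitigation** (RAP 13.3.1): "Unscheduled and withdrawal visit data will be slotted into a scheduled visit window" when that window is otherwise empty.

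RAP 2.1 drops estimation in the G6PD-deficient female subgroup and leaves the treatment difference in haemolysis as the only primary objective. RAP 7.1.2 expects incidence to be low, without a figure.

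**The concern.** A subject with unremarkable values on Days 3, 5, 8 and 15 and an unfilled gap on Day 11 is left out of Table 3.1 and counted as a haemolysis case in Table 3.2. The surrounding values play no part.

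Two consequences follow. First, giving the same value to the missing subjects in both arms is not a worst case for a difference. With similar missingness in the two arms the imputed events largely cancel, so the table can look reassuring however much is missing. Second, when true incidence is low, a modest number of missed visits can outweigh the real events, and unequal attendance can appear as a difference in haemolysis. At stake is whether the one robustness check on the primary result tests the quantity that the RAP calls primary.

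**Working it through.** **1. The plan's own figures.** Protocol 8.2.1 states that "we expect 8% of the total cohort to have a clinically relevant hemolysis". This is 0.5 × 50/300 = 8.3%. Its precision figures reproduce as 1.96 × √(p(1−p)/n):

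- p = 0.50: n = 30 gives 17.9% (stated 18%); n = 15 gives 25.3% (25%).
- p = 0.08: n = 200 gives 3.8% (4%); n = 100 gives 5.3% (5%).

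The 8% rests on 50 deficient females at 50% and nobody else having an event. The RAP has since given up estimating that subgroup because recruitment fell short, so 8% serves here as a high value.

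**2. Inputs.** Five draws (protocol 6.4). 251 subjects randomised (Meta-Analysis Plan, Section 3) at 2:1 (protocol 5.2), about 167 TQ and 84 PQ. *Assumed*, because the documents give no figure: fraction m of draws missed and unfilled, 1% to 5%; haemolysis incidence h, 1% to 8%; misses independent of each other and of haemolysis.

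**3. How much of Table 3.2 could be imputed.** Share of subjects with any missed draw: a = 1 − (1−m)^5, which is 4.9%, 9.6% and 22.6% at m = 1%, 2% and 5%. Table 3.2 rate: h + (1−h)a. Imputed share of the YES subjects: (1−h)a / [h + (1−h)a].

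| h | m | Table 3.2 rate | Share imputed |
|---|---|---|---|
| 1% | 1% | 5.9% | 83% |
| 1% | 5% | 23.4% | 96% |
| 2% | 1% | 6.8% | 71% |
| 2% | 2% | 11.4% | 82.5% |
| 8% | 1% | 12.5% | 36% |
| 8% | 2% | 16.8% | 52.5% |
| 8% | 5% | 28.8% | 72% |

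Imputed events outnumber real ones once a > h/(1−h). With five draws this means m above about 0.2% at h = 1%, 0.4% at 2%, 1.1% at 5% and 1.8% at 8%.

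**4. Whether the difference is bounded.** Take h = 2% and m = 2%. Missing: 0.096 × 167 ≈ 16 TQ and 0.096 × 84 ≈ 8 PQ. Observed events: 2% of 151 ≈ 3 and 2% of 76 ≈ 2 (rounded). Differences are TQ − PQ in percentage points with Newcombe 95% intervals.

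| Imputation | TQ | PQ | Difference (95% CI) |
|---|---|---|---|
| None (observed only) | 3/151 | 2/76 | −0.6 (−7.2 to 3.5) |
| YES in both arms (planned) | 19/167 | 10/84 | −0.5 (−10.0 to 7.3) |
| TQ=YES, PQ=NO | 19/167 | 2/84 | +9.0 (1.9 to 15.0) |
| TQ=NO, PQ=YES | 3/167 | 10/84 | −10.1 (−18.8 to −3.8) |

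The planned row sits beside the observed one, while the data allow either sign with an interval that excludes zero. At m = 1% the planned row is −0.6, against +4.2 and −5.3. At m = 5% it is +0.7, against +23.4 and −22.0.

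**5. Unequal attendance.** With h = 2% in both arms but any-missed shares of 5% and 10%, the table shows 0.98 × (0.10 − 0.05) = 4.9 points where the true difference is zero.

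**The case against.** The case for the plan is substantial. This is an estimation study with no hypothesis test, and each arm's own proportion is reported. For a harm endpoint, counting missing as an event is a recognised worst case for each arm. If little is missing, Tables 3.1 and 3.2 will agree, and that is informative. This stands, and the row should stay.

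The calculation also leans high. Day 3 is an in-hospital visit whose haematology must be reviewed before discharge, so four draws may be more realistic: a = 3.9% and 7.8% at m = 1% and 2%, and 31% rather than 36% imputed at h = 8%, m = 1%. Misses that cluster in the same subjects lower a further, and slotting in other visits reduces missingness. These points change the size of the problem but leave the rule as it is.

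Tables 3.1 and 3.2 share a shell, so Table 3.1 probably shows missing counts by arm, from which a reader could work out opposite bounds. The RAP does not plan or report them.

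A reader might infer that Table 3.2 will measure attendance rather than haemolysis, that nearly all its events will be imputed, or that it can say nothing about the primary estimate. The documents support none of these: they give no missing-data rate and no current incidence, and the per-arm bound is valid.

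**Conclusion.** The point holds in a limited form. From the text alone, the single planned sensitivity analysis bounds each arm's incidence from above but does not bound the TQ–PQ difference, the sole primary objective. That conclusion needs no assumed figure.

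The size does depend on assumptions. With 1–5% of draws missed independently and 1–8% incidence, about 36% to 96% of the YES subjects would be imputed. At 2% and 2%, the range left open runs from about −10 to +9 points, against a planned result near zero. If very few draws go unfilled, the practical effect is small. The primary analysis in Table 3.1 is not called into question by this rule.

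Two wording matters belong with it. Read literally, RAP 13.6.3 also sets to missing a subject with an observed qualifying fall and another missed draw; YES is the correct value there. The cut-off is also inconsistent: before Study Day 17 in 13.7.2.3, up to Study Day 17 in 13.6.3 and the Table 3.2 footnote, and an unfilled placeholder (Study Day X) elsewhere in 13.6.3.

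**What to change.** Amend RAP 13.6.3, 13.7.2.3 and Table 3.2 as follows.

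1. Keep the YES-in-both-arms row, labelled as an upper bound on each arm's own incidence.
2. Add two rows, TQ=YES with PQ=NO and TQ=NO with PQ=YES, using the same Wilson and Newcombe intervals.
3. Show the number of imputed subjects by arm.
4. Score as YES any subject with an observed qualifying fall, whatever other draws are missing, before any imputation.
5. Optionally, add a supportive row that imputes no event for an isolated missed draw with little change from baseline on both sides. State it as an assumption, since bracketing values do not exclude a transient fall. Requiring only that the neighbouring values do not qualify would be too loose: it would treat near-threshold falls as non-events.
6. Leave out a tipping count. If one is wanted, define it as the number of imputed events at which the interval for the difference excludes zero, because the trial has no margin or hypothesis to supply another threshold.
7. Use one cut-off wording throughout.

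The cost is RAP wording and a few table rows, with no new data. The downside is wider stated uncertainty about the difference.
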